3.2 Number of Subjects

90 total: 45 per cohort factoring in a 10% attrition rate

3.3 Eligibility Criteria

Patients must have baseline evaluations performed prior to the first dose of study drug and must meet all inclusion and exclusion criteria. In addition, the patient must be thoroughly informed about all aspects of the study, including the study visit schedule and required evaluations and all regulatory requirements for informed consent. The written informed consent must be obtained from the patient prior to enrollment. The following criteria apply to all patients enrolled onto the study unless otherwise specified.

3.3.1 Inclusion Criteria

1. Patients who are scheduled to undergo therapeutic or prophylactic mastectomy with immediate placement of tissue expanders and have a strong family history or hereditary cancer
2. Age \geq 18 years
3. Zafirlukast is pregnancy category B. There are no adequate and well-controlled trials in pregnant women. Therefore, the effects of zafirlukast on the developing human fetus are unknown. For this reason, women of child-bearing potential must agree to use adequate contraception: 2 methods of birth control, prior to study entry and for the duration of study participation. Should a woman become pregnant or suspect she is pregnant while she is participating in this study, she should inform her treating physician immediately.
4. Ability to understand a written informed consent document, and the willingness to sign it
5. At least 4 weeks post-completion of chemotherapy
6. Adequate organ function within 14 days start of study start:
 - a. Absolute neutrophil count (ANC) \geq 1.5 X 10⁹/L
 - b. Hemoglobin (Hgb) \geq 9g/dL
 - c. Platelets (plt) \geq 100 x 10⁹/L
 - d. Potassium within normal range, or correctable with supplements;

- e. AST and ALT $\leq 2.5 \times$ Upper Limit Normal (ULN) or $\leq 5.0 \times$ ULN if liver tumor is present
- f. Serum total bilirubin $\leq 1.5 \times$ ULN
- g. Serum creatinine $\leq 1.5 \times$ ULN, or 24-hr clearance $\geq 60\text{ml/min}$

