6.1 Screening Assessments

Must be performed from day -28 to day 1, prior to the scheduled mastectomy and tissue-expander placement:

- Medical history
- Physical examination (including height and weight)
- Vital signs (blood pressure, pulse rate, respiratory rate, temperature)
- Con-Med review
- CBC with differential
- Serum biochemical panel including creatinine, fasting glucose, potassium, sodium, chloride, bicarbonate, ALT/AST, total bilirubin
- Blood or urine pregnancy test

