6.2 Assessments and procedures during treatment

Once the patient is confirmed to be eligible based on screening assessments, the following study assessments will be performed. See Table 6 for summary. Cohort A participants will begin treatment with zafirlukast on post-operative day one (+/- 5 days) following placement of tissue expander(s) after the participant is determined safe from a surgical recovery standpoint. Cohort A participants will take zafirlukast twice per day until the patient has completed expansion of the tissue expander. Zafirlukast should be stopped prior to expander implant exchange. Patients will be randomized on the day of surgery by a study personnel other than the surgeon. The surgeon and patient will be informed of the assigned cohort immediately post-surgery.

Research Visits (+/- 1 week)

- Physical examination (including height and weight)
- Vital signs (blood pressure, pulse rate, respiratory rate, temperature)
- Con-Med and AE review
- CBC with differential and platelet count
- Serum biochemical panel including creatinine, fasting glucose, potassium, sodium, chloride, bicarbonate
- Liver function tests: alkaline phosphatase, ALT/AST, total bilirubin (only for Cohort A)

Expander-Implant Exchange

- Tissue specimen collection

End of Treatment (14 days (+/- 3 days) of expander-implant exchange)

- Medical history, physical examination (including height and weight), vital signs (blood pressure, pulse rate, respiratory rate, temperature)
- CBC with differential and platelet count
- Serum biochemical panel including creatinine, fasting glucose, potassium, sodium, chloride, bicarbonate
- Liver function tests: alkaline phosphatase, ALT/AST, total bilirubin (only for Cohort A)
- Con-Med and AE review

Follow up

Patients are followed for two years after implant reconstruction. After implant exchange we will see patients every 2 weeks for the first month, every month for the subsequent 4 months, and, every 6 months for the remainder of the two years. For those patients removed from the treatment, they will be followed as per our standard of care which is monthly for the first six months and then every six months for a total of two years.

- Physical examination (including height and weight), vital signs (blood pressure, pulse rate, respiratory rate, temperature)

Table 6. Schedule of Study Procedures and Assessments

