6.9 Prohibited Concomitant Medications

Subjects are prohibited from receiving the following therapies during the Screening and Treatment Phase of this trial:

- Anti-cancer systemic chemotherapy or biological therapy

Subjects who, in the assessment by the investigator, require the use of any of the aforementioned treatments for clinical management should be removed from the trial. Subjects may receive other medications that the investigator deems to be medically necessary.

Potential Drug Interactions:

The following drug interaction studies have been conducted with zafirlukast

- Co-administration of multiple doses of zafirlukast (160 mg/day) to steady-state with a single 25 mg dose of warfarin (a substrate of CYP2C9) resulted in a significant increase in the mean AUC (+63%) and half-life (+36%) of S-warfarin. The mean prothrombin time increased by approximately 35%. The pharmacokinetics of zafirlukast were unaffected by co-administration with warfarin.

- Co-administration of zafirlukast (80 mg/day) at steady-state with a single dose of a liquid theophylline preparation (6 mg/kg) in 13 asthmatic patients, 18 to 44 years of age, resulted in decreased mean plasma concentrations of zafirlukast by approximately 30%, but no effect on plasma theophylline concentrations was observed.
- Co-administration of zafirlukast (20 mg/day) or placebo at steady-state with a single dose of sustained release theophylline preparation (16 mg/kg) in 16 healthy boys and girls (6 through 11 years of age) resulted in no significant differences in the pharmacokinetic parameters of theophylline.
- Co-administration of zafirlukast dosed at 40 mg twice daily in a single-blind, parallel-group, 3-week study in 39 healthy female subjects taking oral contraceptives, resulted in no significant effect on ethinyl estradiol plasma concentrations or contraceptive efficacy.
- Co-administration of zafirlukast (40 mg/day) with aspirin (650 mg four times daily) resulted in mean increased plasma concentrations of zafirlukast by approximately 45%.
- Co-administration of a single dose of zafirlukast (40 mg) with erythromycin (500 mg three times daily for 5 days) to steady-state in 11 asthmatic patients resulted in decreased mean plasma concentrations of zafirlukast by approximately 40% due to a decrease in zafirlukast bioavailability.

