9.1 Analyses Plans

This is an intention to treat analysis. All patients who were randomized will be evaluated.

Data will be summarized using descriptive statistics by study cohorts. For continuous variables, descriptive statistics will include the number of non-missing values, mean, standard deviation, median, minimum and maximum. For categorical variables, descriptive statistics will include counts and percentages per category by study cohorts.

Primary analysis:

The primary objective of the trial is to determine the capsule contracture between the two study cohorts and the primary efficacy outcome in this trial is capsule thickness at the time of expander-implant exchange. Capsule thickness will be determined by averaging thickness from three separate specimens per patient. The capsule thickness will be analyzed by study cohorts, and t-tests and descriptive statistics with mean, standard deviation and 95% confidence intervals will be used for significance. Missing data will not be imputed. An alpha level of 0.05 will be considered significant for the primary endpoint. For exploratory analysis, the primary endpoint of capsule thickness will be presented as mean \pm SEM and evaluated using analysis of variance (ANOVA) with factors including study cohort, radiotherapy and length of drug treatment.

Secondary Analysis:

For secondary objectives of the trial, we will determine the level of fibrosis and presence of collagen from the biopsy specimens. The level of fibrosis and the presence of collagen will be analyzed descriptively as continuous levels and as ordinal levels with mean, standard deviation and 95% confidence intervals. The difference in the level of fibrosis and relative presence of collagen between study cohorts will be compared using t-tests for significance.

Similar statistical methods will also be employed to analyze the capsule tissue that is removed at the time of expander-implant exchange to determine the level and presence of collagen, fibroblasts and myofibroblasts.

Confounding Factors:

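### Eligibility (3.3) does not exclude women with systemic anti-cancer therapy already planned for the treatment phase, yet section 6.9 says they should be removed after randomisation

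*Combined protocol and SAP*

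**What the plan says.** Protocol section 3.3.1, item 1, admits "Patients who are scheduled to undergo therapeutic or prophylactic mastectomy with immediate placement of tissue expanders", so women with cancer are enrolled as well as prophylactic cases. Item 5 is the only criterion on anti-cancer drugs: "At least 4 weeks post-completion of chemotherapy". It gives no reference date. No inclusion criterion, and none of the six exclusions in 3.3.2, mentions biological therapy or planned post-operative systemic therapy.

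Section 6.9 states: "Subjects are prohibited from receiving the following therapies during the Screening and Treatment Phase of this trial". The listed item is "Anti-cancer systemic chemotherapy or biological therapy". Subjects who, in the investigator's assessment, "require the use of any of the aforementioned treatments for clinical management should be removed from the trial".

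On timing, section 6.1 places medical history and "Con-Med review" before mastectomy, and section 6.2 states: "Patients will be randomized on the day of surgery by a study personnel other than the surgeon". Table 6 runs the treatment period to about week 17 (days 113-119, as needed). Capsule tissue is collected only at expander-implant exchange.

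On analysis, section 9.1 describes an intention-to-treat analysis: "All patients who were randomized will be evaluated". It also says that missing data are not imputed. Section 9.0 allows for 10% attrition and does not list what the allowance covers.

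**The concern.** Section 3.3 decides who enters, and section 6.9 decides who must leave. The two do not use the same rule. Take a woman having a therapeutic mastectomy whose post-operative chemotherapy is already planned at screening. Nothing in 3.3 keeps her out, and at screening she is not yet receiving anything that 6.9 prohibits. She is randomised, may start zafirlukast, and comes under the removal rule once the planned therapy falls due in the treatment phase.

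Her loss was foreseeable before randomisation. It takes a randomised place and probably leaves no capsule measurement. It also sits badly with the commitment to evaluate everyone randomised. In Cohort A, it means giving study drug to someone who is not expected to complete the course.

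**Working it through.** **The rules applied to each type of patient**

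| Patient at screening | Section 3.3 | Section 6.9 | When the loss falls |
|---|---|---|---|
| Chemotherapy or biological therapy already planned for the treatment phase, none being taken now | Not excluded | Removal once she requires it | After randomisation; foreseeable |
| Biological therapy being taken now | Not excluded | Already in breach during screening; visible at the con-med review | Before randomisation, if 6.9 is applied as written |
| Need recognised only after surgery | Not excluded | Removal once she requires it | After randomisation; not foreseeable |

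Only the first row is an avoidable loss after randomisation. In the second row the defect is that 3.3 is silent.

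**Inputs for the size** (section 9.0): two-sided alpha 0.05, t-test, means 2.4 and 1.2 mm, SD 2 mm, 45 per arm randomised, 10% attrition. The share affected, p, is not in the documents. I assume 5%, 10% and 20%.

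**Formula.** Standardised difference d = 1.2/2 = 0.6. Power comes from the noncentral t distribution with noncentrality d × √(n/2) and 2n − 2 degrees of freedom, where n is the number evaluable per arm.

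**The plan's own figure.** At n = 45 the noncentrality is 0.6 × √22.5 = 2.85 and power is 80.4%. The stated 45 evaluable per cohort for more than 80% power reproduces.

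**Baseline after planned attrition.** n = 45 × 0.90 = 40.5, power 76.0%. This drop from 80.4% is not due to the present point. It arises because 45 per arm is both the number enrolled and the number needed evaluable.

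**Adding removals under 6.9.** n = 45 × 0.90 × (1 − p):

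| p (assumed) | n per arm | Power | Change from 76.0% |
|---|---|---|---|
| 5% | 38.5 | 73.8% | about 2 points |
| 10% | 36.5 | 71.4% | 4 to 5 points |
| 20% | 32.4 | 66.2% | about 10 points |

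**Effect of a pre-randomisation check on accrual.** Section 9.0 expects about 80% of 60 women a year, so over two years 60 × 0.80 × 2 = 96. If 10% are screened out, 96 × 0.90 = 86.4 remain to randomise. Without the check, 90 are randomised and 10% removed, leaving 90 × 0.90 = 81. The gain within the planned window is about 5 patients before other attrition. After 10% other attrition, the per-arm numbers are 86.4 × 0.90 / 2 = 38.9 (power 74.3%) with the check and 36.5 (71.4%) without it.

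**The case against.** **Item 5 already bars these women, because someone whose chemotherapy lies ahead is not past completion.** This does not stand. Read that way, item 5 would also bar every woman who has had no chemotherapy, including the prophylactic cases that item 1 admits. The workable reading is a washout for those who have had chemotherapy, and that says nothing about future treatment. On any reading, item 5 does not reach biological therapy.

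**Women on continuing biological therapy are lost after randomisation too.** A reader might infer this from the silence of 3.3, but the documents do not support it. Section 6.9 covers screening, and the con-med review comes before surgery, so the rule as written removes such a woman before she is randomised.

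**A removed patient need not be a lost endpoint.** This stands in part. Section 7.0 says that capsule is normally excised at exchange as standard of care, and 9.1 intends to evaluate all randomised patients. But 6.9 says removal from the trial, not only from study drug, and no section provides for collecting a specimen from a woman so removed. A lost endpoint is likely, not stated.

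**The power loss is overstated.** This stands if 74%, 71% or 66% is compared with 80%. Most or much of that gap comes from the planned attrition, and only the increments from 76% belong here. The 10% allowance might also already include removals under 6.9. The plan does not itemise it; if it does include them, the increments shrink.

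**Many needs emerge only after surgery.** True. No eligibility rule can prevent those losses, so the avoidable group is limited to therapy already planned at screening.

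**Conclusion.** Sections 3.3 and 6.9 conflict for one identifiable group: women for whom systemic chemotherapy or biological therapy during the treatment phase is already planned at screening. They pass eligibility, can be randomised, and are then due for removal, probably before the single endpoint measurement. For women already on biological therapy, the only defect is that 3.3 does not repeat what 6.9 requires.

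The cost is about 2, 4 to 5 or 10 points of power for an affected share of 5%, 10% or 20%. These figures rest on an assumed share, on removed women giving no specimen, and on these removals coming on top of the 10% allowance. The documents settle none of the three. The direction is clear and the correction is cheap, so it should be made.

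**What to change.** Reconcile 3.3 with 6.9. Whatever prohibition the sponsor keeps should also stand as an eligibility criterion, checked before randomisation, for therapy that is ongoing or already planned. It should use the therapies that 6.9 names and the screening and treatment window that 6.9 uses. The sponsor should say when that window ends: section 3.1 puts the last dose on the day before exchange, while 6.2 and 6.4 tie the end of treatment to completion of expansion. The sponsor should also state the reference date for inclusion 5. Which clinical rule applies is for the sponsor to decide. Needs that arise after surgery stay under 6.9, and the plan should say whether a woman removed under it still provides a capsule specimen for the intention-to-treat analysis.

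The cost is a line or two in 3.3 and one screening question. The eligible pool shrinks slightly: at a 10% share, about 86 of the roughly 96 women expected over two years, so reaching 90 could need slightly longer accrual. The women screened out are those whom 6.9 would remove anyway.

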3.3.2 Exclusion Criteria

1. Any significant medical condition, laboratory abnormalities, which places the subject at unacceptable risk if he/she were to participate in the study
2. Currently on a leukotriene inhibitor or used within the past 6 months
3. Prior chest wall radiation
4. Pregnant or breastfeeding
5. Hepatic impairment as defined by:
 - AST(SGOT) $> 2.5 \times$ institutional ULN and ALT(SGPT) $> 2.5 \times$ institutional ULN
6. Has known psychiatric or substance abuse disorders that would interfere with cooperation with the requirements of the trial.

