Patients should be told that a rare side effect of zafirlukast is hepatic dysfunction, and to contact their physician immediately if they experience symptoms of hepatic dysfunction (e.g. right upper quadrant abdominal pain, nausea, fatigue, lethargy, pruritus, jaundice, flu-like symptoms, and anorexia). Liver failure resulting in liver transplantation and death has occurred in patients taking zafirlukast.

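### On the same blood sample, exclusion 5 cancels inclusion 6e's liver-tumour allowance for AST and ALT (up to 5.0 × ULN), in part or in full depending on how its *and* is read (minor)

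*Combined protocol and SAP*

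**What the plan says.** Section 3.3 says that patients "must meet all inclusion and exclusion criteria", and that the criteria cover everyone enrolled except where something else is specified.

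Section 3.3.1, item 6, asks for adequate organ function within 14 days of study start. Item 6e limits AST and ALT to 2.5 × ULN, or to 5.0 × ULN "if liver tumor is present". Item 6f caps "Serum total bilirubin" at 1.5 × ULN.

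Section 3.3.2, item 5, excludes hepatic impairment, defined as "AST(SGOT) $> 2.5 \times$ institutional ULN and ALT(SGPT) $> 2.5 \times$ institutional ULN". It names no tumour exception and no time window.

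On the drug's liver risk, Section 4.1 (Patient Care Implications) says that "a rare side effect of zafirlukast is hepatic dysfunction" and also that "Liver failure resulting in liver transplantation and death has occurred in patients taking zafirlukast".

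No other section reconciles the two enzyme limits.

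**The concern.** The two lists give a liver-tumour patient different limits for the same tests, and both must be satisfied. What remains of the allowance depends on one conjunction, and neither reading gives a sensible rule. Read literally, a tumour patient with AST 4.9 and ALT 2.4 × ULN is eligible, while one with both enzymes at 2.6 is not. Read as *or*, 6e grants something that exclusion 5 always takes back. Two screeners could decide differently about identical patients.

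At stake is a consistent eligibility rule for a small group. There is also a secondary safety point: under the literal reading, a tumour patient with one enzyme as high as 5.0 × ULN can be randomised to a drug with a stated hepatic risk.

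**Working it through.** The plan states no figure to reproduce; the check is one of logic.

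**Inputs.** The limits are 2.5 and 5.0 × ULN (6e) and 2.5 × ULN with no exception (exclusion 5). Both lists apply (Section 3.3). Assumption: both criteria are judged on the same blood sample.

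**Set-up.** Sort each enzyme into three bands: at most 2.5, above 2.5 up to 5, and above 5 × ULN. With and without a liver tumour this gives 3 × 3 × 2 = 18 cells. These are logical combinations, not patient counts.

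**Rules.**
- 6e is met if AST ≤ L and ALT ≤ L, with L = 2.5, or L = 5.0 with a tumour.
- Exclusion 5, literal reading: AST > 2.5 and ALT > 2.5.
- Exclusion 5, *or* reading: AST > 2.5 or ALT > 2.5.
- Eligible = 6e met and exclusion 5 not met.

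**Cells that meet 6e.** One without a tumour and 2 × 2 = 4 with one, so 5 in all. Without the allowance there would be 2, so 5 − 2 = 3 depend on it.

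| Tumour | AST (× ULN) | ALT (× ULN) | Eligible, literal | Eligible, *or* |
|---|---|---|---|---|
| No | ≤ 2.5 | ≤ 2.5 | Yes | Yes |
| Yes | ≤ 2.5 | ≤ 2.5 | Yes | Yes |
| Yes | > 2.5 to 5 | ≤ 2.5 | Yes | No |
| Yes | ≤ 2.5 | > 2.5 to 5 | Yes | No |
| Yes | > 2.5 to 5 | > 2.5 to 5 | No | No |

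The other 13 cells fail 6e under any reading.

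**What exclusion 5 adds.**
- Literal: it is met in 2 × (2 × 2) = 8 cells, of which 7 already fail 6e. It acts alone in 8 − 7 = 1, leaving 5 − 1 = 4 eligible. The allowance is cancelled in part (1 of 3 cells).
- *Or*: it is met in 2 × (9 − 1) = 16 cells, of which 13 already fail 6e. It acts alone in 16 − 13 = 3, leaving 5 − 3 = 2 eligible. The allowance is cancelled in full (3 of 3 cells).

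**After deleting the tumour clause.** L = 2.5 for everyone, so 2 cells are eligible under either reading. The change removes 4 − 2 = 2 cells under the literal reading (tumour, exactly one enzyme above 2.5 up to 5) and 2 − 2 = 0 under the *or* reading.

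**The case against.** Four objections deserve an answer.

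**The edit does not change the outcome for the patients in conflict.** This stands. Under the literal reading the only conflict cell, a tumour with both enzymes above 2.5 up to 5, is ineligible before and after. The two cells removed are ones where the lists agree: 6e admits them and exclusion 5 is silent. Under the *or* reading the edit only tidies the text. Its value is a single rule that does not depend on one word.

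**The documents do not favour 2.5 over 5.0.** This also stands. Adding the tumour exception to exclusion 5 would remove the inconsistency equally well, with all 5 cells that meet 6e eligible under either reading. A reader might infer that 2.5 was the intended limit for tumour patients; no section says so. The preference for it is a judgement.

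**There is no safety gap.** A reader might infer that the mismatch lets patients with liver impairment onto the drug. It does not: where the lists disagree, exclusion 5 keeps the patient out. The remaining point comes from the 6e allowance itself, and nothing in the documents shows 5.0 × ULN in one enzyme to be unsafe. Other protections exist: exclusion 1 bars laboratory abnormalities "which places the subject at unacceptable risk"; 6f caps bilirubin; patients are told which hepatic symptoms to report; unacceptable adverse events end treatment (Section 6.4); and Table 6 schedules liver tests for Cohort A at week 5 and end of treatment. They narrow the point without closing it. Exclusion 1 is discretionary, 6f does not limit AST or ALT, and the rest act after dosing starts.

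**Exclusion 5 is not purely redundant.** A reader of the table might infer that its only role is to cancel the allowance and that patients without a tumour can never be touched by it. That holds only on a single sample. Item 6 has a 14-day window, exclusion 5 has none, and screening may begin at day −28 (Section 6.1). A patient without a tumour whose enzymes are both above 2.5 × ULN on day −24 and both at or below it on day −7 meets 6e yet could still trigger exclusion 5.

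One counter-argument fails. The proviso in Section 3.3 about what is otherwise specified does not let 6e override exclusion 5, because exclusion 5 specifies no exception and the same section requires every criterion to be met.

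**Conclusion.** The inconsistency is real and minor. On one blood sample, the liver-tumour allowance in 6e loses 1 of its 3 cells if *and* is literal and all 3 if it means *or*. Patients in conflict are already excluded, so the only people whose eligibility would change are liver-tumour patients with exactly one enzyme above 2.5 and up to 5 × ULN, under the literal reading.

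Very few such patients, possibly none, are expected. That is an assumption, since the documents give no count. It rests on the setting of mastectomy with immediate expander placement; on inclusion 1, which as worded also asks that patients "have a strong family history or hereditary cancer"; and on Section 6.9, under which anyone needing systemic chemotherapy or biological therapy during screening or treatment should be removed. Efficacy, power and alpha are not affected.

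**What to change.** In 6e, delete the 5.0 × ULN alternative for patients with a liver tumour, so that 2.5 × ULN applies to each enzyme. On one sample this yields the same eligible set under either reading of exclusion 5. The limit is proposed because exclusion 5 already uses it and because it is the more cautious choice given the hepatic warning in Section 4.1.

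Changing *and* to *or* in exclusion 5 is optional, for consistency; on the same sample it alters nobody's eligibility once the clause is gone.

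The cost is one deleted clause in an amendment. No new test is needed, because ALT and AST are already in the screening panel (Section 6.1). The downside is that, under the literal reading, a rare liver-tumour patient with one raised enzyme becomes ineligible.
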